PLWH can be powerful change agents for HIV prevention within communities. Our research suggests that as PLWH receive ART and restore their health, they are motivated to protect their social network members and engage in prevention advocacy (i.e., encourage friends and family to seek HIV testing and care and reduce HIV risk); however, the quality of this advocacy is hampered by challenges related to message content, style and timing of delivery, and the selection of appropriate recipients for advocacy. With effective advocacy training, mobilizing PLWH to be change agents within their networks has the potential to be a “game changer” for HIV prevention, particularly in high-prevalence settings where virtually every family is touched by HIV. In the proposed research, we will conduct a randomized controlled trial (RCT) of *Game Changers*, an 8-session peer-led group intervention that aims to empower and mobilize PLWH to be agents for HIV prevention in their social networks. By decreasing stigma among PLWH and their social network members, as well as training PLWH on key strategies to engage social network members in discussions around HIV, *Game Changers* provides PLWH with the tools to do prevention advocacy and is facilitated by peers who are from participants’ communities and living with HIV. *Game Changers* was developed through an NIMH-funded R34 in partnership with the Infectious Diseases Institute (IDI), a public-private partnership in Kampala that provides care to PLWH, that trains healthcare workers on HIV care and treatment, and conducts research to address the HIV epidemic. As part of the intervention development process, the team conducted focus groups with PLWH and social network members, and engaged with community stakeholders, including a community advisory board. Our pilot RCT with 98 PLWH and 57 social network members revealed promising preliminary intervention effects on reduced internalized stigma and increased HIV-serostatus disclosure to social network members among PLWH, as well as increased condom use and HIV testing among social network members.

The **Specific Aims** are:

1. To conduct a fully powered RCT of *Game Changers* to test intervention effects on the primary outcomes of increased HIV testing, reduced condomless sex, and decreased enacted HIV stigma among social network members of participating PLWH.

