try to contact alters, nor incentivize enrollment with alternative forms of assessment (e.g., phone, home visit, etc.). In the proposed study, we will have resources to hire staff to focus on alter interviews, and to make multiple call attempts, interview alters by phone, reimburse alters for transport, and travel to interview alters outside of Kampala; plus, unlike in the pilot, in the proposed study when an alter is unable to be reached, we will ask the index participant to refer additional alters for us to contact. With these changes, we expect a much higher rate of alter recruitment in the proposed study; nonetheless, our recruitment and power analysis procedures accounted for a potential 50% enrollment rate of referred alters.

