
Randomized Controlled Trial of *Game Changers*

Overview. The proposed design is an individually randomized group-treatment trial using a clustered design.⁹⁶ We will recruit 210 PLWH and randomize 105 to the intervention and 105 to a no-intervention control arm. Each PLWH will be asked to recruit social network members (alters to whom they have disclosed) (736 total, 368/arm). All participants will complete assessments at baseline, and 6, 12 and 18 months post-baseline to assess improved HIV prevention behaviors within the network, mediators of improved behaviors, and HIV outcomes. Participants will be divided into 7 cohorts of 30 (within each cohort, 15 intervention and 15 control). Intervention implementation for the 7 cohorts will be staggered, such that two will be conducted at a time (i.e., 60 PLWH and 210 alters for two cohorts at a time), except the last wave in which there will be one cohort of 30. [name] will oversee the implementation of the intervention program, while [name] will oversee the assessment, data collection and analysis components of the trial.

Randomization. A blocked 1:1 randomization design with stratification by gender (with randomly alternating blocks of 2, 4, and 6 to prevent anticipation of condition) will ensure balance across arms. All groups will be mixed sex (with approximately equal numbers of men and women/group), and a male and a female facilitator will conduct each group. The statistician will use a random number generator to devise a randomization log and a set of sealed numbered randomization envelopes (to prevent condition foreknowledge). After completing the baseline survey, the interviewer will open the corresponding envelope and record the condition. Although individual randomization entails contamination risk, this type of group intervention—where recipients attend several sessions that use structured content and group interaction to target multiple aspects including internalized stigma, comfort and skills with disclosure, and how and who to engage in advocacy with—is less conducive to contamination. Statistical models suggest $\geq 30\%$ of the control arm must receive the equivalent of a full-strength intervention to result in meaningful contamination,⁹⁷ so with a

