To recruit alters, during the baseline social network assessment (see below), we will elicit the names of 20 alters in the PLWH's social network, and ask PLWH to identify alters who know their serostatus. In our prior studies, 87% were able to list 20 alters, and 96% were able to list at least 16 alters. At the end of the interview, PLWH will be asked to select, from the list of alters who know their serostatus, up to 7 alters whom they would be willing to refer to the study; this should be feasible, as the pilot revealed that an average of 13 of the 20 alters knew the participant's HIV status. If they refer more than 4 alters, we will randomly select 4 to target for recruitment (to limit selection bias), although we aim to recruit an average of 3.5 alters per index participant, given that we do not expect to be able to recruit 4 alters from all participants. The decision to recruit 4 is based on a need to balance interviewing enough alters to be sufficiently representative of the person's network, while also being feasible to collect the data from the large sample of overall alters in a longitudinal design. We will request that the PLWH call each selected alter at the end of the interview, and to describe the study opportunity in the presence of the interviewer, who can then immediately schedule a study visit. If any of the 4 refuse to participate or cannot be reached, we will randomly select additional alters on the list of those referred from the index participant until 4 have agreed and enrolled; if only 4 were referred, we will ask the PLWH to refer additional alters, if possible. To enhance alter enrollment, we will allow for phone-based interviews and for staff to travel to meet alters outside of Kampala after the first study visit, and provide a sufficient incentive to cover transport costs; nonetheless, our request for index participants to refer up to 7 alters allows for a 50% alter enrollment rate, in order to achieve our goal of enrolling 3.5 alters per index participant. Given the large number of alters (105/cohort; 210 for two cohorts at the same time), alters will be interviewed over a 2-month period (~25-30 alters per week) at baseline and follow-up. We used similar procedures successfully in our pilot.

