Assessment: Overview. Under the leadership of [name] (MPI), the assessment was developed to include individual-level survey questions for PLWH and alters, and a social network assessment for PLWH only. The 60-75 min. assessment for PLWH and 20-minute assessment for alters will be administered at baseline and months 6, 12, and 18. The 6-month interim period is consistent with the Ugandan Ministry of Health recommendation for repeated HIV testing every 6 months (one of our primary outcomes), and the 18-month follow-up period will allow us to better assess durability of effects. Participants will receive 30,000 Ush (~\$8) per assessment, and 30,000 Ush (~\$8) transportation reimbursement for each intervention session. We will collect tracking information (phone numbers, mapped addresses, contacts for family/friends with whom they have frequent contact). Clinic staff, including “Linkage Facilitators” (i.e., expert patients identified by IDI clinic staff who track patients) will help to track patients that we have difficulty reaching (if participants consent). In our other 12-month longitudinal studies of PLWH in Uganda, we have achieved $\geq 90\%$ retention, and retention in our R34 pilot was $> 95\%$ for both PLWH and alters at the final month-8 follow-up. Assessments will be administered on laptops using Egoweb,¹⁰¹ social network and survey data collection and analysis software developed at RAND. The assessments include the following sections, which we have refined across multiple studies in the US and Uganda (and translated into Luganda; alphas below provided from Ugandan studies).

Individual-Level Outcomes. Sexual Behavior (condomless intercourse) in the past 6 months will be assessed with standard items on number of partners; number of times engaged in intercourse (vaginal or anal) and of those, number of times a condom was used; and perceived HIV serostatus of partner(s).

Alters' HIV Testing (among alters of negative or unknown serostatus) will be assessed. At every time-point, alters will report whether they have been tested for HIV and if so, the date of their most recent test and result,¹⁰⁰ and whether they intend to get tested in the next 6 months (1, not at all, to 5, very much) or start HIV care and ART (if warranted). Self-reported HIV testing and status has been found to be reliable.¹⁰¹⁻¹⁰⁴

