Due to Uganda's law against homosexuality and high societal homophobia, we will take further steps during the informed consent process to protect PLWH who engage in same-sex sexual behavior or who identify as a sexual minority. When clients are screened individually by the coordinator, they will be informed of the eligibility criteria and told that there are legal risks to clients who self-identify as having had sex with or current sexual attraction for someone of the same sex, and if they choose to participate, they may place themselves at risk of inadvertently disclosing their sexual orientation if they advocate to people in their social network about HIV. Specifically, as we did in our pilot study, we will tell participants, "If you choose to participate, it is important to consider the legal risks of participation for people who have had sex with or current sexual attraction for someone of the same sex and for commercial sex workers. You should not say anything in the intervention sessions that you want to keep private from others, and you should not talk about illegal activities in the intervention sessions or when you advocate to people in your social network about HIV." The PLWH then will be told that he/she is welcome to take the consent form home for consideration, after which he/she can contact the coordinator for formal screening, if still interested. This allows sexual minority clients to withdraw their interest without disclosing their sexuality. Alternately, if patients would like to enroll at

that time, we will enroll them on the day we approach them. In addition, to decrease risk and ensure confidentiality, we will not record participants' sexual orientation or same-sex sexual behavior, even if a participant volunteers such information. Such information would put participants at legal and social risk. Thus, even if data were subpoenaed or seized by government officials, participants who engage in same-sex sexual behavior would not be identifiable. We have found these enrollment procedures to be feasible in our R34 pilot, and no potential participant or enrolled participant in our pilot disclosed same-sex sexual behavior.

Psychological Distress. Participants will be referred to a counselor at the clinic if warranted and/or desired by the participant. Participants also have the right to refuse to answer specific questions and can end their participation in the study or intervention at any time.

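### The interviewer opens the randomisation envelope, and nothing keeps the arm from the staff who recruit alters and collect the interview-based primary outcomes

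*Combined protocol and SAP*

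**What the plan says.** **Allocation.** The Randomization paragraph describes sealed, numbered envelopes prepared by the statistician from a log with varying block sizes. It then states: "After completing the baseline survey, the interviewer will open the corresponding envelope and record the condition". The survey meant is that of the index participant (the PLWH).

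**Alter recruitment.** Under Recruitment, index participants choose the alters they will refer at the end of the baseline interview. They are asked to phone the selected alters there and then and to "describe the study opportunity in the presence of the interviewer, who can then immediately schedule a study visit". Whether the envelope is opened before or after these calls is not stated. Alters who refuse or cannot be reached are replaced, with further referrals requested if needed. Alter interviews are spread over about two months, at baseline and at follow-up.

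**Outcomes.** Aim 1 names the primary outcomes as "increased HIV testing, reduced condomless sex, and decreased enacted HIV stigma among social network members of participating PLWH". For testing, "alters will report whether they have been tested for HIV". For condomless sex, "Sexual Behavior (condomless intercourse) in the past 6 months will be assessed with standard items on number of partners". Enacted stigma is different: under Network Composition, the index participant reports on each alter.

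**Staff.** The Informed Consent text mentions a coordinator ("When clients are screened individually by the coordinator"), and Preliminary Studies says "we will have resources to hire staff to focus on alter interviews". The available text does not describe masking of interviewers, separate follow-up interviewers, or restricted access to the recorded condition.

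**The concern.** Sealed envelopes protect concealment up to the moment of assignment. They do nothing for what follows, and in this trial much of the data-critical work follows. The primary outcomes concern alters, and alters may still be being called, replaced and interviewed at baseline when the arm is already known to an interviewer.

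Two things are at stake.

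- **Who is enrolled.** Repeat call attempts, replacement draws and requests for further referrals all depend on staff effort, which could differ by arm. The pilot gives a reason to watch this. It reports 35 alters from intervention participants and 21 from controls (these sum to 56, against 57 stated), with 51 and 47 index participants: 35/51 = 0.69 and 21/47 = 0.45 alters per index participant. The cause is not given, and alter recruitment was added to the pilot post hoc, so this is not evidence of interviewer bias. It shows only that alter yield can differ by arm.
- **What is recorded.** Sexual behaviour, testing and stigma are sensitive topics asked by staff. The plan abstracts records for viral load and diagnosis date, and for PrEP when obtained at the study clinic. It describes no record check for the primary outcomes. Sandwich standard errors and dropout weights do not correct reporting that differs by arm.

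**Working it through.** **Step 1. Who can know the arm at each stage.**

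| Stage | Staff involved | Is the arm kept from them? |
|---|---|---|
| Index baseline survey | Interviewer | Yes; the envelope opens afterwards |
| Alter referral calls | Interviewer present | Not stated; order relative to envelope not given |
| Alter baseline, about two months | Alter-interview staff; overlap with envelope openers not stated | Not stated |
| Follow-up at 6, 12 and 18 months | Not identified | Not stated |

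Only the first row is protected. The envelope rule itself is explicit; what is missing is any barrier after it.

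**Step 2. The plan's own effective sample size.** Statistical Power starts from 736 alters with about 15% attrition: 736 × 0.85 = 625.6, taken as 625. With 3.5 alters per index participant, m = 3.5 × 0.85 = 2.975 retained alters per cluster.

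- ICC .01: 625 / (1 + 1.975 × 0.01) = 612.9 (plan: 612)
- ICC .05: 625 / (1 + 1.975 × 0.05) = 568.8 (plan: 568)

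Both reproduce. The stated .80 power does not: 65% versus 54.7% with 306 per arm gives .74 at two-sided 5% (alpha assumed, since none is stated). That is a separate matter, and the illustration below does not use it.

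**Step 3. Illustration of an arm-dependent reporting shift.** Assume no true effect, a 65% rate in both arms, 1:1 allocation, and reporting shifted by b in one arm only. The documents give no value for b; 2, 3 and 5 percentage points are assumptions.

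SE = sqrt(2 × 0.65 × 0.35 / (n/2))

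- n = 612: sqrt(0.455 / 306) = 0.0386
- n = 568: sqrt(0.455 / 284) = 0.0400

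False-positive rate = P(|Z + b/SE| > 1.96)

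| b | n = 612: b/SE | rate | n = 568: b/SE | rate |
|---|---|---|---|---|
| 0.02 | 0.52 | 8.1% | 0.50 | 7.9% |
| 0.03 | 0.78 | 12.2% | 0.75 | 11.6% |
| 0.05 | 1.30 | 25.4% | 1.25 | 23.9% |

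Letting the variance move with the shifted rate gives 8.1%, 12.0% and 24.8% for n = 612, and 7.9%, 11.5% and 23.3% for n = 568, which is essentially the same picture.

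**Step 4. What the illustration covers.** It treats month 18 as a single cross-section, whereas the planned model tests a timepoint-by-arm interaction over repeated measures. It also counts any arm-dependent shift, including participants' own social desirability. It is therefore a scale for the problem, not an estimate of what masking would save.

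**The case against.** The strongest reply is that the documents show silence after the envelope, not a demonstrated flaw, and that several safeguards are already present.

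- A reader might infer that the interviewer who opens the envelope also takes that participant's alter outcomes. The documents do not say so, and staff dedicated to alter interviews are planned. This stands: the supportable statement is that nothing prevents it.
- A reader might infer that moving the envelope would mask interviewers. It would not do so reliably. Index participants know their arm, interviewers are staff of the clinic that hosts the study, and the assessments ask about contact with intervention peers, about discussions between index participant and alter, and about advocacy with each alter. This stands too.
- It is tempting to describe all primary outcomes as self-reports. Enacted stigma is reported by the index participant, who knows the arm. Interviewer masking leaves that person's own bias untouched.
- Standard items on laptops limit discretion, and alters are drawn at random when more than four are referred. Both help. Neither governs call effort, requests for additional referrals, or how a sensitive question is put.
- Alters are not randomised, and nothing says they are told the arm. This favours the change: two of the three primary outcomes come from people whose interviewers could realistically be kept unaware.

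The reply narrows the point but does not remove it. The plan assigns knowledge of the arm to an interviewing role and gives no reason for doing so.

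**Conclusion.** The point holds in this form: the plan gives the allocation to an interviewer, sets no barrier between that knowledge and alter recruitment, alter baselines or follow-up, and relies on interview reports for every primary outcome. A better procedure is available using roles that the documents already mention, so it should be adopted.

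The size of the bias cannot be derived from the documents. Under the stated assumptions, shifts of 2, 3 and 5 points give false-positive rates of about 8%, 12% and 24-25% for condomless sex. For scale, 3 points is 3/10.3 = 29% of the difference the trial is designed to detect at ICC .01. Only the interviewer-driven part of such a shift would be removed.

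A reader might conclude that the change costs nothing. The documents do not support that: the coordinator appears only in screening, with no workload given, and the number of interviewers is not stated.

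**What to change.** - Have a planned staff member who collects no outcomes, for example the coordinator, open the envelope and record the condition, after the index baseline survey and the initial alter referral calls are complete. State this order in the Randomization and Recruitment paragraphs.
- Keep the condition log from interviewers. Do not tell the arm to the planned alter-interview staff or, where the rota allows, to those who do index follow-up interviews.
- Place items that can reveal the arm (peer contact, sessions, advocacy discussions) after the primary outcome items where the questionnaire permits. Ask participants not to disclose their arm, and record when an interviewer learns it.
- Report alter referral and enrolment by arm.
- State who remains unmasked, and acknowledge that participants' own reporting bias remains, notably for enacted stigma.

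The cost is some rota and coordination work, and someone must be available when each baseline visit ends. It is likely low, though the documents do not allow it to be put at zero. Sample size and power are unchanged.

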*Game Changers Pilot RCT.*⁸³ 98 PLWH and 57 alters participated in the pilot RCT across four intervention-control cohorts (with a wait-list control group).⁸³ The pilot intervention was the same as the intervention outlined below for the proposed study. Participants were interviewed at baseline and ~5-months and ~8-months post-baseline. Results showed high feasibility, acceptability, and preliminary effects, consistent with our conceptual model. In terms of feasibility, of the 98 participants recruited (51 intervention, 47 control), 97 (99%) and 93 (95%) completed assessments at months 5 and 8, demonstrating very high retention. Retention was also high in intervention sessions, with 60% of the intervention group attending all sessions and each session attended by an average of 76% of participants. Reasons for missed sessions included being out of town, conflicting work/school schedules, sick or caring for someone sick, moved, and transportation issues.

To test the feasibility of recruiting alters, we asked each of the 98 PLWH to refer up to 3 alters; 214 alters were referred by 89 (91%) PLWH (average of 2.3 alters (out of max. of 3) referred by each, suggesting little difficulty in identifying alters to recruit). However, since alter recruitment was added post-hoc to the study design (and with no designated funding in the budget), we decided to try to contact only 135 alters. Of the 135 alters, 17 (13%) were already enrolled (15 as PLWH, 2 as alters) and thus were ineligible, and 1 was withdrawn. Of the remaining 117, 34 (29%) could not be reached (did not answer the phone or had a nonworking number); and 26 (22%) declined because they were busy, lived far, or were sick. Thus, 57 alters (49%) were enrolled; 35 from intervention participants and 21 from control participants. The characteristics of the recruited alters (61% female, 32% family, 68% friends, 14% sex partners; 43% HIV+) were similar to that of all alters listed in the index participant networks (53% female, 37% family, 63% friends, 4% sex partners; 28% HIV+), which increases confidence that the recruited alters represent the larger network. We did not repeatedly

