multi-component, multi-session intervention like Game Changers it is highly unlikely that casual communication between intervention and control participants could result in meaningful contamination. We will assess and control for whether control participants communicated with intervention peers about intervention content.

Eligibility Criteria for PLWH include (1) ≥ 18 years-old, (2) in care for > 1 year (because they are more likely to be medically stable, adjusted to their HIV diagnosis, and ready to engage in advocacy), and (3) disclosed their HIV status to at least one person. All PLWH also will be patients at IDI's clinic, where they will be recruited. Clients will be excluded if they participated in the intervention as part of the prior R34 pilot study.

Eligibility Criteria for Alters include (1) ≥ 18 years-old; (2) referred by a PLWH enrolled in the study; (3) know the PLWH's serostatus; and (4) willing/able to do the first study visit in person. (After initial screening/baseline visit, other alter study visits can be done by phone, or interviewers can travel to meet alters.) As described below, PLWH will be asked to recruit up to 4 alters for participation in assessments.

Recruitment. As in the pilot, to recruit PLWH: (1) clinic staff and expert patients (who work with clinic staff to track patients) will refer eligible patients to interviewers, who will be in the waiting area of the clinic on weekdays (M-F) every day during the recruitment period for each cohort; and (2) interviewers (who will be IDI staff) will approach all patients in the waiting area on the same designated days, to inform them of the study. Interviewers will cross-check the names of referred patients with IDI clinic records to verify that they are patients at IDI who have been in care for > 1 year and disclosed to at least one person. In the pilot, only one person was screened ineligible due to the disclosure criterion. Because we will enroll two intervention-control cohorts at a time, we need to recruit 60 participants at a time (30 per cohort) or per wave of recruitment; each wave of recruitment will take place over 3 months (30 PLWH and 105 alters enrolled and surveyed per month, 1.5 PLWH and 5-6 alters per day), followed by a 3-month period when the intervention and attention control program are implemented with the two cohorts, and no further recruitment until the next wave of recruitment in the next quarter (see Timeline).

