Statistical Power. We calculated power for alter reports of condomless sex at month 18. Based on the pilot, we assume 65% of control alters will report condomless sex at month 18. Starting with 736 alters, and assuming ~15% attrition by month 18 (which is conservative, based on 98% alter retention over 8 months in the pilot, and <10% attrition over 12 months in our other studies in Uganda), we will have 625 alters; accounting for within-ego clustering gives us an effective sample size of 612 for ICC=.01 or 568 for ICC=.05. For ICC=.01, we will have .80 power to detect a group difference of 10.3% (i.e., an intervention rate of 54.7%), and for ICC=.05, we will have power to detect a 10.7% group difference. These differences represent small effect sizes (Cohen's $d = .23\text{--}.24$). For PLWH index participants, using pilot data, we estimate the ICCs of our secondary outcomes to be small-to-moderate (0-.16), and assume 15% attribution and 7 intervention groups (either Game Changers or attention control), with an average cluster size of 12.9 (90 intervention participants/7 groups).^{96, 140, 141} After accounting for within-group correlations, we will have 80% power to detect medium to large differences (.41-.58 SD, based on the outcome) between the study arms at follow-up.

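### The contamination argument covers control PLWH rather than the alters who carry the primary outcomes, and the power calculation makes no allowance for exposed control alters

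*Combined protocol and SAP*

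**What the plan says.** The Specific Aims place all three primary outcomes (HIV testing, condomless sex, enacted stigma) in social network members.

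The Randomization section accepts that individual randomisation carries a contamination risk. It cites modelling that at least 30% "of the control arm must receive the equivalent of a full-strength intervention to result in meaningful contamination", and concludes that casual communication is very unlikely to reach that level with a multi-session programme. It adds: "We will assess and control for whether control participants communicated with intervention peers about intervention content".

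The pilot RCT description reports that, of the 135 alters the team tried to contact, "17 (13%) were already enrolled (15 as PLWH, 2 as alters").

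Statistical Power sizes the trial on alters' condomless sex: "we assume 65% of control alters will report condomless sex at month 18", a figure taken from the pilot. "Starting with 736 alters, and assuming ~15% attrition by month 18", 625 remain, and "accounting for within-ego clustering gives us an effective sample size of 612 for ICC=.01 or 568 for ICC=.05". From this, "we will have .80 power to detect a group difference of 10.3% (i.e., an intervention rate of 54.7"%), and at ICC .05 "we will have power to detect a 10.7% group difference". No term for exposed control alters appears.

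**The concern.** The argument in Randomization concerns what a control PLWH could pick up of an eight-session group programme. An alter in either arm never receives that programme. What reaches an intervention alter is encouragement from a trained PLWH, and a control alter who also knows a trained PLWH can receive the same thing by the intended route. The section does not consider this path.

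The plan's own account makes the path plausible. All PLWH come from one clinic, networks are described as dense and interconnected, participants are taught to favour popular and bridging alters, and alters are encouraged to pass information on. The pilot's 15 of 135 shows that trial PLWH appear in one another's networks.

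Exposure of control alters would lower the control rate of condomless sex and shrink the contrast. A real effect could then be missed, and a null result could not be told apart from diffusion into the control arm. A 30% cut-off would label exposure of 10% or 20% as not meaningful although it has a visible cost in power.

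**Working it through.** **Inputs.** All are from Statistical Power unless noted: control rate .65; effective n 612 (306 per arm) at ICC .01 and 568 (284 per arm) at ICC .05; printed differences 10.3 and 10.7 points; stated power .80. Allocation is 1:1 (Randomization). Alpha and sidedness are not stated, so two-sided .05 is assumed.

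**1. Effective sample size.** Mean cluster 625/210 = 2.976. 625/(1 + 1.976 × .01) = 612.9 and 625/(1 + 1.976 × .05) = 568.8. The plan's 612 and 568 reproduce.

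**2. Stated power.** Two-proportion normal formula, with p̄ the mean of the two rates:

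power = Φ{ [ |p1 − p2| − 1.96 √(2p̄(1 − p̄)/n) ] / √( p1(1 − p1)/n + p2(1 − p2)/n ) }

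- .65 vs .547, n = 306: Φ[(.103 − .0777)/.0394] = .74.
- .65 vs .543, n = 284: Φ[(.107 − .0807)/.0409] = .74.

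The stated .80 is not reproduced. A fall from 65% needs 11.1 points (n = 306) or 11.5 points (n = 284) for .80. One-sided .05 gives .83 for the first comparison, or .81 with continuity correction. Measured upward from 65%, the detectable differences are 10.34 and 10.71 points, which match the printed values. That suggests the difference was computed in the upward direction, but this is an inference.

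**3. Exposure model.** A share c of control alters takes a fraction f of the full effect d. The control rate becomes .65 − c·f·d and the intervention rate stays at .65 − d. Full effect (f = 1) is the worst case.

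**4. Results at full effect** (two-sided .05; the same to two decimals at both effective sample sizes):

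| Exposed control alters | From the stated .80 (11.1- or 11.5-point fall) | From the printed rates |
|---|---|---|
| 0% | .80 | .74 |
| 10% | .71 | .65 |
| 20% | .61 | .54 |
| 30% | .49 | .44 |

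The shortcut Φ[2.80(1 − c) − 1.96], which needs no choice of difference, gives .71, .61 and .50 at 10, 20 and 30%.

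**5. Half effect.** With f = .5, 20% exposure gives c·f = .10, the 10% row: about .71 from the stated .80.

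**6. Larger effect.** In the pilot, condomless sex with main partners fell by 7.7 points in intervention alters and rose by 10.5 in controls, a contrast of 18.2. With d = .182 and full-effect exposure of 30%, the control rate is .65 − .3 × .182 = .595 against .468. Power is .89 (n = 306) or .86 (n = 284).

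**7. What is measured.** Potential Mediators asks alters about HIV-related discussions with people they know, and about discussions between the PLWH and alter. As described, neither item isolates encouragement received from someone other than the referring PLWH.

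**The case against.** Several counter-arguments have force.

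- **The 65% may already include some contamination.** It comes from a pilot RCT at the same clinic with wait-list controls, and the 10.3 points is a detectable between-arm difference. A reader might infer that the plan assumed wholly unexposed control alters. The documents do not say so; they only make no allowance.
- **The plan itself calls 30% meaningful.** The loss at 30% therefore does not contradict it. Only the range below 30% bears on the point.
- **Full effect in every exposed alter is a worst case.** The pilot report says PLWH did not advocate with every alter interviewed, so acquaintance is not exposure. An effect near 18.2 points would survive even 30%. That contrast, however, comes from a pilot with 57 alters (p = .08), and the trial is sized on about 10 points.
- **The pilot overlap gives no contamination rate.** A reader might turn 15 of 135 into one. Those 15 were ineligible as alters because they were already enrolled, and their arms are not given. The figure shows that overlap exists, not how many control alters would be exposed.
- **Alters are asked about advocacy, and contamination will be assessed.** It would go too far to say alter exposure is unmeasured, and the reference to control participants could be read to include alters. The remaining gap is narrower: the source of the advocacy is not identified. Adjusting for communication that happens after randomisation also does not restore power, and it conditions the primary comparison on a post-randomisation variable.

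**Conclusion.** The concern stands in limited form. The justification for individual randomisation does not address the route by which control alters could be exposed, and the sample size makes no allowance for it. On the stated .80, the cost is about 9 points of power at 10% exposure and about 19 at 20%, assuming a two-sided .05 test and full effect in each exposed control alter. At half effect the 20% loss falls to about 9 points. On the printed rates the series starts at .74, so the difference and power in that section must be reconciled before any sensitivity range is quoted. The true degree of exposure is unknown from the documents, and a large true effect would leave adequate power. The case is therefore for stating the dependence and measuring exposure, not for concluding that the trial is underpowered or that individual randomisation was wrong.

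**What to change.** 1. **Wording and power.** Reconcile the printed differences with the .80, and state alpha and sidedness. Remove 30% as the cut-off for meaningful contamination. State in Statistical Power that the figures make no allowance for exposed control alters, and give the 10% and 20% results as a sensitivity range.

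2. **One alter item at follow-up.** Ask whether anyone other than the referring PLWH encouraged the alter about HIV testing or condom use, and report it by arm. Word it neutrally: it must not ask about programme attendance or anyone's HIV status, since either could disclose another person's serostatus.

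3. **Baseline link indicator.** Build it from the baseline network lists and referral and tracking data, matched by the data manager blind to arm once enrolment closes. It cannot be completed before randomisation because cohorts are staggered and envelopes are opened straight after each baseline survey. Prespecify a sensitivity analysis of the primary outcomes in unlinked networks, in place of adjusting the primary model for post-randomisation communication. Intent-to-treat stays primary.

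**Cost.** The stated power becomes less favourable and the alter survey gains one item. Matching will be imperfect because the lists hold first names and last initials, and it needs care because personal identifiers are stored apart from research data.
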